- Describe the causes of non-performance of the confirmatory test and identification of predictors of non-performance or postponement of the diagnostic test within a maximum period of 90 days from the initial recommendation.

Study design

Overview

Study, prospective, open, randomized, controlled.

Justification of the main elements of the protocol

The FINDRISC screening questionnaire has been previously studied and validated, can be applied quickly, economically and its low complexity makes them widely available (5,10). Similarly, previous studies have shown that periodontal disease is related to the appearance of alterations in the glycemic profile so that up to 30% of adults over 30 years of age who attend general dentistry consultations are identified as a population at risk (3).

Despite the drawbacks to its mass application, OGTT remains included within the current CPGs and continues to be a reference test for the diagnosis of patients with DM2 (3).

Measurement of A1c may be more convenient than OGTT, particularly if performed at the point of care (POC-A1c). Additionally, the characteristics for its implementation and its technical profile are clearly established. However, its impact on the screening algorithm under real conditions of use is unknown and its profile for inclusion within a mass screening system has not yet been established.

Setting the primary endpoint

While it is possible to perform screening using any of the validated questionnaires, in real conditions of their implementation a second visit of the patient is required to perform a confirmatory test (GTT) and the loss to follow-up is required a major challenge for health systems. It is proposed that the implementation of POC-A1c can contribute to improving the follow-up rate in the context of population screening and facilitate the successful implementation of large-scale screening campaigns.

Therefore, the primary outcome is the probability of going to OGTT according to the strategy implemented.

Choice of comparator

Currently, the screening guidelines contemplate the completion of the FINDRISC questionnaire followed by a confirmatory test carried out in the centralized laboratory. Because of this, the recommended practice is established as a comparator.

Type of design

Prospective, open label, randomized, controlled study in adults with no known diagnosis of diabetes.

Study procedures

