- **Bias in outcome measurement:** the outcome of the OGTT sampling is sufficiently robust not to be affected by the research team, the participant itself or external factors.
- **Bias in the selection of the reported result:** at this point it is mentioned how the creation of surrogate outcomes not proposed in the protocol will be avoided and how consistency will be maintained in terms of the applicability of statistical terms, that is, only what is proposed in the data analysis will be carried out.

Statistical analysis plan

Description of statistical methods

For the primary objectives, the proportions of patients who attended the performance of the GTT in each of the groups will be obtained and the statistical significance test will be applied for superiority in the follow-up ratio of the intervention group (A) over the control group (B). Additionally, descriptive statistics will be obtained regarding the dynamics of application of the confirmatory test (i.e., latency time).

The variables will be checked for normality using the Kolmogorov-Smirnoff test. For quantitative variables, data shall be expressed as mean and standard deviation, or median and interquartile range 25%-75%, as the case may be.

For qualitative variables, proportions (%) will be determined. The continuous data between both groups will be analyzed with the T test if the distribution of the variables is normal or with the Mann-Whitney test if they are not. The analysis of the categorical data between two groups will be carried out with the chi-Square or Fisher test as appropriate.

An analysis will be carried out on the conditional probability of reaching a OGTT test: $P(\text{perform OGTT} | \text{FINDRISC} \geq 12)$

$P(\text{perform OGTT} | \text{POC-A1c} \geq 5.7\% \text{ and FINDRISC} \geq 12)$

An analysis will be performed to identify risk factors for not performing the PGT, the dependent variable will be dichotomous. The main independent variable will be dichotomous corresponding to the control and intervention group. The control variables will be: age,

	
Effectiveness comparison of the hemoglobin measurement glycosylated at the point of care (POC-A1c), vs the standard current based on tolerance test oral to glucose, for the detection early of Diabetes Mellitus guy 2 (DM2) in Colombia. EDDIT-1 STUDY
	
Version: 3.0 Date: February 15, 2022

---	--	---

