gender, type of affiliation, FINDRISC score and POC-A1c value (for those in which it is available) and others that are considered possible variables of confusion.

In order to analyze these associated factors, it is proposed to carry out a generalized linear model of binomial type or poisson type with robust errors, in order to evaluate the influence of the factoris sociodemographic and with relevance / biological and contextual plausibility in the aforementioned outcome (non-realization of OGTT). The partnership measures will be presented through RR with their corresponding 95% confidence interval. A bivariate and multivariate analysis will be carried out to identify possible confusion or interaction for which the probability of performing the OGTT should be adjusted. Under the methodology proposed by Furnival-Wilson (1974) a reduced model will be estimated, using the logarithmic probabilities of the candidate models in order to establish the most parsimonious model. The goodness of fit of the models and the assumptions underlying the selected methodology will be evaluated. The statistical package where the analyses will be carried out is Stata 16MP.

Sample size

The study is designed to detect a 10% difference in going to the laboratory for OGPT between the intervention group (60%) and the control group (50%) considering a power of 80% and a confidence interval range of 95%.

Considering that some people with positive FINDRISC (i.e., greater than or equal to 12) will have a normal APOC-A1c, the number of participants in the intervention group (i.e., group A) will be increased by 30% to ensure sufficient subjects available for analysis with completely positive classification. This percentage corresponds to patients without glycemic alterations or DM2 identified in the FINDRISC validation study (9).

According to this and considering that the primary endpoint is a categorical variable, an initial sample of 784 randomized subjects (392 in each arm) was calculated, after the adjustments the sample is of 902 subjects distributed asymmetrically (510 in group A or intervention and 392 in group B or control).

It is expected that the proportion of patients with FINDRISC greater than or equal to 12 will be 30% of the patients to whom the questionnaire is applied, according to this the expected total of Sieved patients is 3005. However, the total number of patients screened can be extended to complete the goal of randomized patients.

Level of significance

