According to the described methodology, the significance level for the primary objective is 0.05.

Procedure to Explain Missing Data

Any deviation from the statistical plan will be discussed with all authors for approval.

Selection of subjects to be included in the analyses

The final analysis will include all individuals with complete data.

Ethical considerations

The research group will submit to the Ethics Committee for consideration all required documentation from the study, explain the risks and benefits and ask for their written consent. Each participant shall have the right to leave the study when he/she so arranges. The study will follow the Good Clinical Practice regulations of the Helsinki Declaration. An adverse effects data collection sheet will be used, it is estimated that possible adverse effects will be related to taking capillary puncture for POCA1C (puncture site infection and pain or dizziness/vomiting).

Data management and record keeping

Data management and record keeping will be carried out in accordance with the current procedures of MetricsMed and a specific parameterization is contemplated for the implementation of this project.

Financing and insurance (budget and schedule of activities)

	
Effectiveness comparison of the hemoglobin measurement glycosylated at the point of care (POC-A1c), vs the standard current based on tolerance test oral to glucose, for the detection early of Diabetes Mellitus guy 2 (DM2) in Colombia. EDDIT-1 STUDY
	
Version: 3.0 Date: February 15, 2022

---	--	---

See annex budget 5.

Publication Policy

The publications will be based on data from the center, analyzed according to the protocol. Researchers undertake not to publish data obtained in a centre or in a small group of centers before the main publication (or updates of the same), unless they are formally accepted by all other researchers. Authorship, order of authors, publications and results of the study shall be determined in accordance with the authors according to international standards for publications.

[figure not shown]
Annexes

1. Flow of interventions and procedures
2. Informed consent
3. FINDRISC Questionnaire
4. Table of variables
5. Schedule of activities – Budget

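### The primary comparison of OGTT attendance uses no baseline covariates; a pre-specified adjusted risk difference would be a cheap gain in efficiency, probably a small one

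*Combined protocol and SAP*

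**What the plan says.** The endpoint is binary: "Therefore, the primary outcome is the probability of going to OGTT according to the strategy implemented" (Setting the primary endpoint). For the primary objective, Description of statistical methods obtains the proportion attending in each group, after which "the statistical significance test will be applied for superiority in the follow-up ratio of the intervention group (A) over the control group (B"). That paragraph names no test, covariate, effect measure or confidence interval. A general sentence further down the same section says "The analysis of the categorical data between two groups will be carried out with the chi-Square or Fisher test as appropriate".

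The section then plans a regression of not doing the OGTT, the complement of the primary endpoint. Arm is its main independent variable. The control variables are age, "gender, type of affiliation, FINDRISC score and POC-A1c value (for those in which it is available"), plus any others thought to confound. It is a binomial or Poisson model with robust errors, reported as RR with 95% CI, and is cut down to a parsimonious model by the Furnival-Wilson method. The section also mentions adjusting the probability of doing the OGTT for any confounding or interaction found. It frames all this as a search for risk factors and does not call it primary.

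Bias Control describes simple randomisation and names no stratification factor. Age and FINDRISC are eligibility items. Date of birth, gender and health coverage are in Annex 4.

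**The concern.** When randomisation is not stratified, baseline factors that predict the outcome add noise to the comparison of raw proportions. If age, sex, affiliation or FINDRISC score predict attendance, an estimate adjusted for them has a narrower interval and, once standardised, still targets the same difference in proportions. The data are collected anyway.

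The planned regression looks as if it might fill this role, but it cannot as written, for three reasons:

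- **POC-A1c.** It is measured only in group A, after assignment. The plan analyses individuals with complete data, so a complete-case fit with this term would drop group B and leave no arm contrast.
- **Covariates.** The list is left open.
- **Selection.** The reduced model is chosen from the data, and the usual interval would ignore that choice.

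At stake is some precision in the primary result, and a stated primary effect size with an interval.

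**Working it through.** **Inputs.** From Sample size and Level of significance: 60% v 50%; power 80%; "the significance level for the primary objective is 0.05"; "an initial sample of 784 randomized subjects (392 in each arm) was calculated"; then 510 in group A and 392 in group B. Sidedness is not stated. R², the share of outcome variance explained by the covariates, appears nowhere in the documents, so 1% to 10% is an assumption.

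**1. The plan's own figure.** Two-sided pooled formula, no continuity correction:

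n = [1.96√(2 × 0.55 × 0.45) + 0.8416√(0.25 + 0.24)]² / 0.10² = (1.379 + 0.589)² / 0.01 ≈ 387.3, so 388 per arm.

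With variance 0.25 in both arms and the two z values summing to 2.80, n = 2 × 0.25 × 2.80² / 0.01 = 392 exactly. A one-sided test gives 305. The stated size is therefore a two-sided calculation without covariates. Group A: 392 × 1.3 = 509.6, rounded to 510; total 902.

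**2. Unadjusted power at 510:392.**

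- Pooled proportion = (306 + 196) / 902 = 0.5565.
- SE under the null = √[0.5565 × 0.4435 × (1/392 + 1/510)] = 0.03337.
- SE under the alternative = √(0.25/392 + 0.24/510) = 0.03329.
- Power = Φ[(0.10 − 1.96 × 0.03337) / 0.03329] = Φ(1.039) = 85.1%.
- CI half-width = 1.96 × 0.03329 = 6.53 percentage points.

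At 392:392 the power is 80.5%.

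**3. Effect of adjustment.** Both standard errors are multiplied by √(1 − R²). The equivalent number of participants saved is 902 × R².

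| Assumed R² | Power | CI half-width (points) | Equivalent saving of 902 |
|---|---|---|---|
| 0 | 85.1% | 6.53 | 0 |
| 1% | 85.4% | 6.49 | 9 |
| 2% | 85.8% | 6.46 | 18 |
| 5% | 86.8% | 6.36 | 45 |
| 10% | 88.5% | 6.19 | 90 |

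The gain is 1.7 points at 5% and about 3.5 points at 10% (88.53 − 85.06).

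**4. Simulation check.** Logistic standardisation with four covariates at 392/510, 3,000 runs per setting, unadjusted then adjusted power:

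- no prognostic value: 84.4%, 84.5%;
- R² about 1%: 84.6%, 84.9%;
- about 2%: 86.3%, 86.9%;
- about 6%: 83.5%, 86.1%;
- about 11%: 84.2%, 88.8%.

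The Monte Carlo standard error of each figure is about √(0.85 × 0.15 / 3000) = 0.65 points. Adjustment cost nothing when the covariates were useless.

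**5. Size of chance imbalance.** The standard deviation of a standardised baseline difference is √(1/392 + 1/510) = 0.067, so imbalance is usually small.

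**6. If some outcomes are lost.** The sample size makes no allowance for losses and withdrawn participants are not replaced. With an assumed 15% loss, the standard errors are divided by √0.85 and unadjusted power is 79.0%. R² of 5% brings it to 81.0%, and 10% to 83.0%.

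**The case against.** The strongest reply is that nothing here is wrong. An unadjusted comparison of proportions in a randomised trial is valid, its error rate already allows for chance imbalance, and the design exceeds its power target. That stands in full. A reader might infer that the primary test is biased or that the trial is underpowered for want of adjustment; the documents support neither.

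Four further points also stand, at least in part:

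- **The primary test is inferred.** The chi-square or Fisher sentence is a general rule. No reading of the primary paragraph, however, yields an adjusted analysis.
- **Adjustment is not absent.** A reader might conclude that the plan ignores covariates or never gives an effect size. It plans an arm RR with 95% CI adjusted for these same variables. What is missing is a model fit to serve as the primary treatment effect.
- **The plan does not claim that these variables predict attendance.** It lists them as control variables. FINDRISC is truncated at 12 or more, and age is one of its items (Annex 3), so the two overlap. A large R² cannot be presumed.
- **There is some cost.** Under the complete-data rule, a missing covariate could remove a participant whose outcome is known. Affiliation has three categories in Annex 4 but is labelled dichotomous. Both must be settled first.

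**Conclusion.** The point holds as an optional improvement in efficiency. The primary comparison, as best it can be read, is unadjusted although four baseline variables are to hand, and the existing regression cannot stand in for an adjusted treatment effect.

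The size is modest and uncertain. Over an assumed R² of 1% to 10%, power goes from 85.1% to 85.4%–88.5%. The gain is under 2 points if R² is 5% or less, and nil if the covariates are not prognostic. These figures assume the planned 60% v 50%, a two-sided 0.05 test and all 902 participants analysed. Calling this a known loss of precision would go too far, because the documents give no measure of prognostic strength. A benefit that does not depend on R² is that naming the estimator supplies the effect measure, interval and sidedness that the primary paragraph leaves out.

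**What to change.** Before any comparison of outcomes by arm (the trial is open label, so database lock alone is too loose a limit), amend the primary paragraph as follows:

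- **Estimate:** the marginal risk difference, with the RR alongside, each with a 95% CI, and a two-sided p-value at 0.05.
- **Model:** logistic regression with arm, FINDRISC score, age, sex and affiliation (three categories), standardised over all randomised participants. No POC-A1c term and no variable selection.
- **Missing covariates:** simple imputation, so that nobody with a known outcome is dropped.
- **Supporting analysis:** the unadjusted chi-square test.

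The risk-factor regression can remain as a separate exploratory analysis.

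The cost is a few lines in the plan, slightly more Stata work, and fixing covariate coding and missing-covariate handling in advance. No new data are needed.

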A Pre-Screening activity will be carried out, with prior authorization of use of personal data, where the FINDRISC test will be applied to different population groups and in case the subjects obtain 12 points or more, they will be invited to participate in the study. Otherwise, participants with 11 points or less according to the application of FINDRISC will receive brief information on healthy lifestyles according to their risk group, ending the activity.

Once the Pre-Screening activity has been carried out, to carry out each day, a work site will be installed in the different places established to carry out the screening of the disease that will be attended by a doctor, bacteriologist, and nursing assistant. Subjects at risk identified by FINDRISC will be explained what the study consists of; if they wish to participate in it, and understand, accept, and sign the informed consent: the doctor will proceed to record the relevant data in their medical record, evaluate inclusion and exclusion criteria.

Subsequently, the participants will be randomized into 2 groups. Participants in group A (intervention) will be offered information on healthy lifestyles according to their outcome and will be given a measurement of POC-A1c*. In the participants of group B (control) they will be offered the same information on healthy lifestyles according to their FINDRISC result.

**The work site will have a properly covered cubicle, in which a POC-A1c equipment will be available with the necessary requirements of location and operation to guarantee the validity of the test. In this cubicle will be a laboratory assistant who executes the pre-analytical and post-analytical phase.*

In addition, all randomized participants will be invited to perform a GPOT in the CAIMED partner laboratory or in the laboratory of their choice with the preparation recommendations necessary for the realization of the same. For this purpose, they will be given an order that includes the date of screening, a tracking number and time window in which they must go (i.e., 30 days and with a second attempt-maximum window to 90 days).

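### One secondary objective asks for predictors of postponing the OGTT as well as of not doing it, but the single yes/no predictor model, with no stated cut-off day, cannot separate the two

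*Combined protocol and SAP*

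**What the plan says.** The last item under Secondary objectives asks for the causes of not performing the test and for "identification of predictors of non-performance or postponement of the diagnostic test within a maximum period of 90 days from the initial recommendation".

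Under Study procedures, the test order carries two attendance windows: "30 days and with a second attempt-maximum window to 90 days". Follow-up calls are scheduled at 30 and 90 days, and Annex 4 lists the date of the OGTT as a variable.

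The Description of statistical methods plans one predictor analysis: "An analysis will be performed to identify risk factors for not performing the PGT, the dependent variable will be dichotomous". For its form, "it is proposed to carry out a generalized linear model of binomial type or poisson type with robust errors", reported as risk ratios with 95% confidence intervals. The same paragraph restates the outcome as the OGTT not being carried out. It sets no day at which this is judged and does not mention postponement.

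Timing appears once more in that section, as a description of latency. For continuous variables in general: "The continuous data between both groups will be analyzed with the T test if the distribution of the variables is normal", with Mann-Whitney otherwise. The reasons given in the telephone calls are to be analysed qualitatively.

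**The concern.** The objective names two behaviours and the design has two windows in which to tell them apart, yet the model has one binary outcome. A participant tested on day 85 and one tested on day 3 both performed the test. If the outcome is judged at the end of the 90-day window they get the same code, and a characteristic that slows people down without stopping them looks unrelated to the outcome.

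The protocol itself argues, under Purpose and justification, that time, money and fasting are barriers to attendance. Such barriers may delay as well as prevent. A collected variable such as health coverage or employment status could be reported as not a predictor when it does predict the postponement that the objective asks about.

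**Working it through.** **Inputs from the documents.** Group sizes 510 and 392; planned attendance 60% and 50%; windows of 30 and 90 days. The sample size is not in dispute. The usual two-proportion formula (two-sided 0.05, 80% power) gives 388 per arm against the stated 392, a variance of 0.25 in both arms gives 392.4, and 392 × 1.3 = 509.6, rounded to 510.

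**Inputs assumed.** The documents give no share of late attenders, so every split by day 30 below is illustrative.

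**How many people are concerned.** Expected attenders: 510 × 0.60 + 392 × 0.50 = 306 + 196 = 502. If 20% to 50% attend on days 31-90, that is 0.20 × 502 ≈ 100 to 0.50 × 502 = 251 postponers.

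**Two invented factors.** Factor 1 only delays: 35% v 45% attend by day 30, and 55% in both groups by day 90. Factor 2 only prevents: 30% v 45% by day 30 and 40% v 60% by day 90, so that 10/40 = 15/60 = 25% of attenders are late in both groups.

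| | By day 30 | Days 31-90 | Not by day 90 |
|---|---|---|---|
| Factor 1 present | 35% | 20% | 45% |
| Factor 1 absent | 45% | 10% | 45% |
| Factor 2 present | 30% | 10% | 60% |
| Factor 2 absent | 45% | 15% | 40% |

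**What each analysis returns (present v absent).**

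- *Yes/no outcome cut at day 90.* Factor 1: 0.45/0.45 = 1.00. Factor 2: 0.60/0.40 = 1.50. Delay is invisible.
- *Yes/no outcome cut at day 30.* Factor 1: 0.65/0.55 = 1.18. Factor 2: 0.70/0.55 = 1.27. Both appear, and nothing shows which one delays.
- *Three-level outcome, odds of late v prompt.* Factor 1: (20/35)/(10/45) = 2.57. Factor 2: (10/30)/(15/45) = 1.00. The two are separated.
- *Discrete-time model, ratio of the probability of attending among those not yet tested.* Factor 1: 35/45 = 0.78 in days 0-30, then (20/65)/(10/55) = 1.69 in days 31-90. Factor 2: 30/45 = 0.67, then (10/70)/(15/55) = 0.52. Delay shows as a reversal between intervals. Without a covariate-by-interval term the two interval effects are pooled into one and the reversal is lost.

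**Is the information usable?** Take 902 participants, a factor present in half, and 55% attendance by day 90 at both levels, giving 451 × 0.55 ≈ 248 attenders per level. An unadjusted late-v-prompt comparison then has power of about 0.73 for 20% v 30% late, 0.93 for 30% v 45%, and over 0.99 for 20% v 40%. Rarer factors and incomplete dates would lower these figures.

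**Do other planned analyses fill the gap?** Descriptive latency relates timing to no predictor. The general two-group test, if applied to latency, would compare arms only, unadjusted and among attenders only. The call answers give stated reasons, not a predictor model.

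**The case against.** The strongest reply is that the objective can be read as a single composite: the test was not done within 90 days, whether refused or put off. A binary outcome fits that reading, and the text is a translation. The reading is possible but strained, because it leaves postponement with no meaning of its own in a design with two attendance windows.

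Second, the plan does not ignore timing. Latency is described and may be compared by arm, and reasons are collected at day 30 from everyone not yet tested, including those who attend later. This stands, and it means that the causes part of the objective is served. A reader might infer that half of the objective goes unanswered; that is too strong. What lacks an analysis is the search for predictors of postponement.

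Third, a reader might infer from the Bias Control sentence "only what is proposed in the data analysis will be carried out" that the plan forbids a postponement analysis. It does not. The sentence is aimed at outcomes not proposed in the protocol, and postponement is proposed there. The section headed Procedure to Explain Missing Data also lets deviations go to all authors for approval. But an approved deviation is a weak substitute for specifying the analysis beforehand.

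Fourth, a reader might take it as settled that late attenders are coded with prompt ones. That follows from the natural 90-day reading, but the plan states no cut-off. With a 30-day cut they would join the never-attenders instead.

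**Conclusion.** The mismatch is real and limited. The plan has no analysis that can identify predictors of postponement separately from predictors of non-performance, whichever single cut-off is used. This rests on reading the objective as naming two behaviours, which its wording and the two windows support.

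Its size cannot be fixed from the documents. About 100 to 251 of 502 expected attenders is a range under an assumed late share, and the ratios above are illustrations. One part of one secondary objective is affected; the comparison of attendance between the arms is untouched. It is worth correcting before analysis because the correction is cheap.

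**What to change.** 1. State that the planned binomial or Poisson model is for OGTT not done by day 90, and keep it for predictors of non-performance.
2. Add one pre-specified model for postponement, using the OGTT date in Annex 4 and the inclusion date. Either use a three-level outcome in all randomised participants (done by day 30, done on days 31-90, not done by day 90) and read postponement from the late-v-prompt contrast; or use a discrete-time model with intervals 0-30 and 31-90 days and covariate-by-interval terms.
3. Do not report the risk ratio for not done by day 30, taken alone, as a predictor of postponement: factor 2 in the working gives 1.27 with no difference in timing among attenders.
4. Use covariates available in both arms. The POC-A1c value exists only in group A, and with the analysis limited to complete data a model that includes it would drop group B. Keep it for an analysis within group A.

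The cost is a few sentences in the plan, one more model and one more secondary table. No new data are needed: the inclusion date is already used in the call script, and the screening date is on the test order. The drawback is modest power for the late category, which should be acknowledged when a null result is reported.

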If the answer is I have not taken the test: Could you please tell us why you have not taken the sugar test? Wait for a response, and document it, end the call like this: "Remember that we will call you in 2 months again to confirm if the test was done."

**The answers are recorded by the platform and will be analyzed qualitatively by the researchers.*

Scheduling of study visits (schedule)

Responsible	Prescreening	Visit 1	Phone Call 1 (30 days ± 3 days)	Phone Call 2 (90 days ± 3 days)	Phone Call 3 (30 days after reporting to the center ± 3 days, if applicable)
Doctor Bacteriologist Research Assistant	– Conferences of application of FindRisc as risk screening				
Doctor		Explanation of the study, its procedures and obtaining the consent informed. Review of eligibility criteria.			
Research Assistant		VERIFICATION of FINDRISC, Randomization and data processing on the platform			
Research Assistant		Data processing on the platform to the corresponding group			
Laboratory		Implementation of POC-A1c			

Effectiveness comparison of the hemoglobin measurement glycosylated at the point of care (POC-A1c), vs the standard current based on tolerance test oral to glucose, for the detection early of Diabetes Mellitus guy 2 (DM2) in Colombia. **EDDIT-1 STUDY**

Version: 3.0
Date: February 15, 2022

CRS			Follow-up call 30 days after the PGT request.	Follow-up call - 30-90 days after admission to the study in patients not attending OGTT.	Verification call 30 days from the report of the result of the requested test. To those who present an impaired OGMP and have requested a control doctor.

Bias Control

- **Bias derived from the randomization process:** it is carried out through the Office - Excel platform by means of algorithms for the generation of random numbers and their assignment to the specific group, by means of a simple impaired randomization; in order to maintain the masking of the assignment, a number (1-2) will be assigned to classify the intervention and its comparator, keeping this hidden from most researchers.
- **Bias due to deviations from planned interventions:** from study design, with simple randomization, the subject who has received a group assignment cannot move on to the other.
- **Bias due to the lack of outcome data:** The number of stratified lost data of intervened versus non-intervened will be evaluated, if it exceeds 5% analysis and data imputation will be made.

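### The secondary model for not performing the OGTT combines study arm with POC-A1c, which only group A has; fitted on complete data it loses every control and cannot give an adjusted arm RR

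*Combined protocol and SAP*

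**What the plan says.** One of the Secondary objectives asks for "identification of predictors of non-performance or postponement of the diagnostic test within a maximum period of 90 days". It is not limited to either arm.

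Description of statistical methods answers this with a binomial or Poisson generalised linear model with robust errors. The outcome is not performing the OGTT, and associations are reported as RR with 95% CI. On arm it says: "The main independent variable will be dichotomous corresponding to the control and intervention group". The control variables are age, gender, type of affiliation, "FINDRISC score and POC-A1c value (for those in which it is available"), and other possible confounders. A reduced model is then chosen by the Furnival-Wilson method, "using the logarithmic probabilities of the candidate models in order to establish the most parsimonious model".

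Study procedures decides who has a POC-A1c value. Group A receives lifestyle information "according to their outcome and will be given a measurement of POC-A1c". For the other arm: "In the participants of group B (control) they will be offered the same information on healthy lifestyles according to their FINDRISC result". The Synopsis says the same, and Bias Control rules out moving between groups.

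Selection of subjects to be included in the analyses states: "The final analysis will include all individuals with complete data". Bias Control has an imputation rule with a 5% trigger ("The number of stratified lost data of intervened versus non-intervened will be evaluated"), but it is the item on missing outcome data.

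**The concern.** Whether a POC-A1c value exists is fixed by randomisation: group A has it by design and group B does not. A model that needs both arm and POC-A1c on every row therefore has no control rows left, and the coefficient it was built to estimate disappears. The bracketed qualifier recognises that some values are absent but gives no rule for handling them.

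Two things are at stake. First, the adjusted RR for arm, which is the model's own main variable. Second, the meaning of the other predictors: they would describe non-attendance only among people given POC-A1c, while the objective covers everyone at risk. The model selection step is also affected, because candidates with and without POC-A1c do not naturally share a sample.

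**Working it through.** **Inputs.** From Sample size: attendance 60% (A) and 50% (B), 80% power, 95% confidence, 392 per arm initially, then 510 in A and 392 in B. From Description of statistical methods: arm, age, gender, affiliation, FINDRISC score and POC-A1c. From Annex 4: health coverage has three categories but is labelled dichotomous, so both codings are checked.

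**The plan's own figures.** The two-sided pooled formula at 5% gives n = (1.960·√(2·0.55·0.45) + 0.842·√(0.24 + 0.25))² / 0.10² ≈ 388 per arm, close to the stated 392. Then 392 × 1.30 = 509.6, so 510, and 510 + 392 = 902. The planned sizes are reproduced.

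**Rows lost.** A complete-data fit with POC-A1c keeps 510 A and 0 B, so 392/902 = 43.5% are dropped. Expected non-attenders are 0.40 × 510 = 204 in A and 0.50 × 392 = 196 in B, 400 in total. The share lost is 196/400 = 49%.

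**Estimability.** On the remaining rows arm always equals 1 and duplicates the intercept.

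| Model | Rows | Rank / columns, 3-level affiliation | Rank / columns, 2-level affiliation |
|---|---|---|---|
| Arm and POC-A1c | 510 | 7 / 8 | 6 / 7 |
| Arm, no POC-A1c, same rows | 510 | 6 / 7 | 5 / 6 |
| Arm, no POC-A1c, everyone | 902 | 7 / 7 | 6 / 6 |

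The deficiency follows from the design and not from any covariate values.

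**What is lost.** The planned RR of non-attendance is 0.40/0.50 = 0.80. SE(log RR) = √(0.6/204 + 0.5/196) = 0.074, giving an approximate 95% CI of 0.69 to 0.93. The adjusted counterpart of this estimate cannot be obtained.

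For another predictor, assume a binary covariate split evenly, with SE(log RR) = √(2(1−p)/(p·n/2)). With n = 510 and p = 0.40 this is 0.108. With n = 902 and p = 400/902 = 0.443 it is 0.075. The ratio is 1.45.

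**If controls are kept by a coding.** The usual device is arm plus arm × (A1c − reference), with zero in group B. It is full rank on 902 rows, but the arm RR then refers to the reference value. The documents give no A1c distribution or slope, so I assumed a group A mean of 5.8% and SD of 0.5, with a range of slopes. Geometric mean arm RRs from simulated trials of 510 and 392 (400 trials; 300 for the 5.7% row) were:

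| Reference | RR per A1c point 1.0 | 0.9 | 0.7 |
|---|---|---|---|
| Group A mean | 0.80 | 0.80 | 0.79 |
| 5.7% (the plan's impaired cut-off) | 0.80 | 0.81 | 0.82 |
| 6.5% (the diabetes criterion the protocol cites) | 0.80 | 0.74 | 0.62 |

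Hand check at 6.5%: 0.80 × 0.9^0.7 = 0.74 and 0.80 × 0.7^0.7 = 0.62.

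**Model selection.** On a common complete sample, group B is absent from every candidate, including those without POC-A1c. If each candidate instead uses its own available rows (510 or 902), the log-likelihoods are not comparable. At the planned rates group B contributes −271.7 under the binomial (392 × ln 0.5) and −331.9 under the Poisson (196 × ln 0.5 − 196). Leaving group B out raises the log-likelihood by those amounts, against 4.5 (binomial) or 2.5 (Poisson) for the planned arm effect over a common rate.

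**The case against.** The strongest reply is that the authors knew controls have no POC-A1c and said so in the bracket. On that view the variable is meant only for group A, either in its own analysis or as a within-A term. The complete-data sentence would not count a control as incomplete for lacking a test never scheduled in that arm; read that way, it would empty the control group from the primary comparison too. The failure would also be obvious when it occurred (n falls to 510 and arm is constant), so no wrong arm estimate would be published. Arm is randomised, so the primary comparison and bivariate RR already answer the main question.

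Part of this stands. The point concerns one secondary model, and the primary result does not depend on it. The larger coding shifts arise only at a reference far from the group A mean and under assumed slopes; at 5.7% the shift is small. The log-likelihood distortion occurs only if candidates are ranked on different rows, which the plan neither proposes nor excludes.

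The rest does not rescue the specification. A group A model cannot contain the stated main variable. A within-A term is written nowhere. Standard software drops a row with a missing covariate however the complete-data sentence is read. The imputation rule concerns outcomes, and imputing A1c for controls would rest entirely on group A because no control value is observed. Finding the failure at analysis would mean choosing a repair after seeing the data, although Bias Control commits the team to the analyses proposed.

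**Conclusion.** The concern holds. With arm and POC-A1c in one model and rows restricted to complete data, no adjusted arm RR exists. This part is exact and needs no assumption beyond POC-A1c being absent in group B, as the protocol specifies. The counts rest on the planned arm sizes and attendance rates. The 1.45 ratio rests on an evenly split binary covariate, and the coding results on an assumed A1c distribution and slopes. The damage is confined to the secondary predictor analysis: the primary comparison, the bivariate arm analysis and candidates without POC-A1c fitted to all participants remain sound. Because a stated model cannot estimate its own main variable, it should be corrected before analysis.

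**What to change.** Remove POC-A1c from the between-arm model. Fit arm with age, gender, affiliation and FINDRISC score in all randomised participants with outcome data. Other confounders the plan has in mind can be added if they are recorded in both arms. Keep arm in every candidate during selection so that its RR is always reported, and fit all candidates to the same participants so that their log-likelihoods can be compared.

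Add a separate exploratory model in group A only, with POC-A1c value as a predictor of non-attendance and no arm term, and label its results as applying to people who received the test.

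The cost is a few sentences of SAP wording and one extra model. No new data and no change to trial conduct are needed.
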